9.2.2.6. Supraventricular Arrhythmias and Cardiac Conduction Disorders

All events of TE supraventricular arrhythmias and cardiac conduction disorders will be fully evaluated. Patients who develop any event from these groups of disorders should undergo an ECG which should be submitted to the central reading center. Additional diagnostic tests to determine exact diagnosis should be performed, as needed. The specific diagnosis will be recorded as an AE. Events that meet criteria for serious conditions as described in Section 9.2.1 must be reported as SAEs. Study drug should be temporarily discontinued in any patient with signs and symptoms of serious cardiac arrhythmias or conduction disorders. Study drug may be restarted when/if it is safe to do so, in the opinion of the investigator.

9.2.2.7. Acute Gallbladder Disease

Information on the patient's history of gallbladder disease (prior cholecystectomy, history of acute cholecystitis or cholelithiasis) will be recorded on an eCRF at Visit 2. All events of TE biliary colic, cholecystitis, or other suspected events related to gallbladder disease should be evaluated and additional diagnostic tests performed, as needed.

9.2.2.8. Acute Renal Events

Renal safety will be assessed based on repeated renal functional assessment, as well as assessment of AEs suggestive of acute and chronic renal failure.

9.2.3. Complaint Handling

Lilly collects product complaints on investigational products and drug delivery systems used in clinical studies in order to ensure the safety of study participants, monitor quality, and to facilitate process and product improvements.

Patients will be instructed to contact the investigator as soon as possible if he or she has a complaint or problem with the investigational product so that the situation can be assessed, and a product complaint form should be completed.

9.3. Treatment of Overdose

Study drug overdose (more than the specified number of injections) will be reported as an AE. In the event of overdose, refer to the IB and/or Product Label.

9.4. Safety

9.4.1. CV Safety

9.4.1.1. Electrocardiograms

Electrocardiograms will be collected according to the Schedule of Activities (Section 2) and centrally overread. Electrocardiograms should be recorded according to study-specific recommendations included in the Manual of Operations for the study, using standardized equipment provided by the sponsor.

Each ECG tracing will be assessed by the investigator immediately upon recording for clinical management purposes. Any clinically relevant findings from ECGs obtained *before* the first dose of study drug that result in a diagnosis should be reported as a preexisting condition and medical history. Any clinically relevant findings from ECGs that result in a diagnosis and that occur *after* the patient receives the first dose of the investigational treatment should be reported to Lilly or its designee as an AE via eCRF. Results of the central overread will be entered into the clinical trial database and will be used for the statistical analysis of the effects of the randomized treatments. In addition, once the overread ECG is returned from the centralized ECG vendor, the investigator, or qualified designee, is responsible for determining if any change to the patient management is needed. The investigator, or qualified designee, must document his/her review of the ECG printed at the time of evaluation, the final overread ECG report issued by the central ECG laboratory, and any alert reports.

9.4.1.2. Vital Signs

Sitting BP and PR will be measured using standardized equipment provided by the sponsor according to the Schedule of Activities (Section 2). Vital sign measurements should be taken before obtaining an ECG tracing and before collection of blood samples for laboratory testing, at visits where required (see Schedule of Activities, Section 2). The participant should be required to sit quietly for 5 minutes before vital sign measurements are taken. An appropriately sized cuff (cuff bladder encircling at least 80% of the arm) should be used to ensure the accuracy of BP measurements. The arm used for the BP measurement should be supported at heart level. At Visit 1 (screening), to determine which arm should be used to collect BP and PR throughout the study, BP and PR will be measured once in each arm, and the arm that had the higher SBP should be used to collect all 3 measurements of both BP and PR at all study visits. For each parameter (PR, SBP, and DBP), 3 measurements will be taken for each patient at each visit using the same arm; the recordings should be taken at least 1 minute apart, and each measurement of sitting PR and BP will be recorded in the eCRF. Any AE related to changes in BP and PR should be reported.

9.4.2. Laboratory Tests

For each patient, laboratory tests detailed in [Appendix 2](#) should be conducted according to the Schedule of Activities (Section 2).

Specific laboratory measures to be analyzed as exploratory endpoints are listed in Section 4.

Any clinically significant findings from laboratory tests that result in a diagnosis and that occur after the patient receives the first dose of investigational product should be reported to Lilly or its designee as an AE via eCRF.

With the exception of laboratory test results that may unblind the study, Lilly or its designee will provide the investigator with the results of laboratory tests analyzed by a central vendor.

9.4.3. Safety Monitoring

Lilly will periodically review evolving aggregate safety data within the study by appropriate methods, including trends in safety variables, laboratory analytes, and AEs. In addition, the study team will review safety reports in a blinded fashion according to the schedule provided in the Trial-Level Safety Review plan. Lilly will also review SAEs within time frames mandated by company procedures. The Lilly CRP will, as appropriate, consult with the functionally independent Global Patient Safety therapeutic area physician or clinical scientist.

Specific safety measures are included in the protocol to ensure appropriate monitoring of pancreatic (Section 9.2.2.3), thyroid (Section 9.2.2.4), and liver safety (Section 9.4.3.1).

In the event that safety monitoring uncovers an issue that needs to be addressed by unblinding at the group level, only members of the DMC (an advisory group for this study formed to protect the safety of the patients and the integrity of data; refer to Section 10.3.8) will be allowed to conduct additional analyses of the safety data.

9.4.3.1. Hepatic Safety Monitoring

If a study patient experiences elevated ALT $\geq 3 \times \text{ULN}$, alkaline phosphatase $\geq 2 \times \text{ULN}$, or elevated total bilirubin $\geq 2 \times \text{ULN}$, liver testing ([Appendix 4](#)) should be repeated within 3 to 5 days including ALT, AST, alkaline phosphatase, total bilirubin, direct bilirubin, gamma-glutamyl transferase (GGT), and creatine kinase to confirm the abnormality and to determine if it is increasing or decreasing. If the abnormality persists or worsens, clinical and laboratory monitoring should be initiated by the investigator and in consultation with the study medical monitor. Monitoring of ALT, AST, alkaline phosphatase, and total bilirubin should continue until levels normalize or return to approximate baseline levels.

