8.1. Discontinuation from Study Treatment

8.1.1. *Permanent Discontinuation from Study Treatment*

Following randomization, it is expected that patients will remain on study medication for the duration of the Treatment Period (through Visit 11). Patients will be required to permanently discontinue from study drug only in the following circumstances:

- if a patient is inadvertently enrolled and it is determined that continued treatment with study drug would not be medically appropriate (see Section 8.1.3)
- if a patient is diagnosed with an active or untreated malignancy (other than basal or squamous cell skin cancer, in situ carcinomas of the cervix, or in situ prostate cancer) after randomization
- if a patient is diagnosed by the investigator with acute or chronic pancreatitis
- if a patient is diagnosed with C-cell hyperplasia or MTC after randomization
- if a patient develops an eGFR <15 mL/min/1.73 m² (confirmed on retest) as calculated by CKD-EPI
- if the patient or the patient's designee, for example, legal guardian, requests that the patient be withdrawn from study drug
- if the investigator or sponsor decides that the patient should be withdrawn from study drug; if the investigator decides to permanently discontinue study treatment because of an SAE or a clinically significant laboratory value, Lilly or its designee should be alerted immediately
- if the sponsor decides that a treatment arm and patients in that arm should be withdrawn from study drug

Discontinuation of the investigational product for abnormal liver tests **should be considered** by the investigator when a patient meets 1 of the following conditions after consultation with the Lilly designated medical monitor:

- ALT or aspartate aminotransferase (AST) $>8 \times \text{ULN}$
- ALT or AST $>5 \times \text{ULN}$ for more than 2 weeks
- ALT or AST $>3 \times \text{ULN}$ and total bilirubin level $>2 \times \text{ULN}$ or prothrombin time $>1.5 \times \text{ULN}$
- ALT or AST $>3 \times \text{ULN}$ with the appearance of fatigue, nausea, vomiting, right upper quadrant pain or tenderness, fever, rash, and/or eosinophilia ($>5\%$)
- Alkaline phosphatase $>3 \times \text{ULN}$

- Alkaline phosphatase $>2.5\times\text{ULN}$ and total bilirubin $>2\times\text{ULN}$
- Alkaline phosphatase $>2.5\times\text{ULN}$ with the appearance of fatigue, nausea, vomiting, right quadrant pain or tenderness, fever, rash, and/or eosinophilia ($>5\%$)

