9.4.3.1.1. Hepatic Safety Data Collection

Additional safety data should be collected via the eCRF if 1 or more of the following conditions occur:

- elevation of serum ALT to $\geq 5 \times \text{ULN}$ on 2 or more consecutive blood tests
- elevated serum total bilirubin to $\geq 2 \times \text{ULN}$ (except for cases of known Gilbert's syndrome)

- elevation of serum alkaline phosphatase to $\geq 2 \times \text{ULN}$ on 2 or more consecutive blood tests
- patient discontinued from treatment due to a hepatic event or abnormality of liver tests
- hepatic event considered to be a SAE

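### The 3-to-5-day liver retest is not triggered by AST, so one AST-based reason to consider stopping study drug has no directed repeat between Week 36 and Week 52

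*Protocol*

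**What the plan says.** **Retest (Protocol 9.4.3.1).** The rule begins "If a study patient experiences elevated ALT" and sets three triggers: ALT ≥3×ULN, alkaline phosphatase ≥2×ULN, total bilirubin ≥2×ULN. Liver testing "should be repeated within 3 to 5 days including ALT, AST, alkaline phosphatase, total bilirubin, direct bilirubin", GGT and creatine kinase. Then: "If the abnormality persists or worsens, clinical and laboratory monitoring should be initiated by the investigator and in consultation with the study medical monitor". And: "Monitoring of ALT, AST, alkaline phosphatase, and total bilirubin should continue until levels normalize or return to approximate baseline levels". AST is therefore in the retest and in the continued monitoring, but not among the triggers.

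**Stopping study drug (Protocol 8.1.1).** Discontinuation should be considered "by the investigator when a patient meets 1 of the following conditions after consultation with the Lilly designated medical monitor". All four aminotransferase conditions in the list apply to ALT or AST alike. One of them carries a duration: above 5×ULN "for more than 2 weeks".

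**Extra eCRF data (Protocol 9.4.3.1.1).** The aminotransferase condition reads "elevation of serum ALT to" ≥5×ULN on at least two consecutive tests. The other laboratory thresholds are for bilirubin and alkaline phosphatase. Two further conditions cover treatment discontinuation for a liver reason and hepatic SAEs.

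**Schedule (Protocol Section 2, Appendix 2).** The chemistry panel, which includes AST, is drawn at Visit 1, Week 36, Week 52, early termination and Visit 801. It is not drawn at Week 44.

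**The concern.** The stopping list treats AST as equal to ALT, while the rule that produces the follow-up values does not. A stopping consideration with a duration can be applied only if a second value exists. If AST rises alone, the protocol asks nobody to obtain that value before the next scheduled panel, and weekly dosing continues in the meantime. No reason is given for leaving AST out of the trigger. What is at stake is consistent follow-up of individual patients across sites, not the efficacy comparison.

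**Working it through.** The plan states no figure on this point, so the check sets the rules side by side and then counts the scheduled interval.

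**1. Which 8.1.1 aminotransferase conditions need a later AST value?**

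| Condition (ALT or AST) | Later AST needed? |
|---|---|
| >8×ULN | No, one value is enough |
| >5×ULN, lasting more than 2 weeks | Yes |
| >3×ULN with bilirubin >2×ULN or prothrombin time >1.5×ULN | No. The bilirubin arm already starts the retest through bilirubin; the prothrombin arm needs no second AST |
| >3×ULN with listed symptoms or eosinophilia >5% | No, it is met at presentation |

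All four name AST, and one of the four depends on a repeat.

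**2. Which patient falls through?** The patient must meet the >5×ULN level, no other 8.1.1 liver condition and no 9.4.3.1 trigger. That requires all of the following:

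- AST >5 to 8×ULN
- ALT <3×ULN
- alkaline phosphatase <2×ULN
- total bilirubin <2×ULN
- prothrombin time not >1.5×ULN
- no listed symptoms
- eosinophilia ≤5%

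If ALT also reaches 3×ULN, the retest starts and the gap disappears.

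**3. When does it matter?** Visit 1 precedes dosing. Week 52 ends treatment, and Visit 801 is off drug. Week 36 is therefore the only scheduled on-treatment panel followed by further dosing for a patient who stays in the study. An early termination visit would include chemistry, but a raised AST does not prompt one.

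**4. How long is the scheduled gap?**

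- Nominal: 52 − 36 = 16 weeks; 16 × 7 = 112 days.
- Windows of ±7 days at each visit: 112 − 14 = 98 days (14 weeks) to 112 + 14 = 126 days (18 weeks).
- Weekly dosing: 16 doses at nominal timing.

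**5. What would a trigger achieve?** More than 2 weeks means day 15 or later, so a retest at days 3 to 5 does not settle the criterion by itself. It opens the continued monitoring, which can settle it. The frequency of that monitoring is not stated.

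**6. Does any other provision direct the repeat?**

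| Provision | What it does |
|---|---|
| 9.2 | Laboratory reports are reviewed and the review documented; medically important AEs are followed, at a frequency the investigator chooses |
| 8.1.2 | Drug may be interrupted for a laboratory value judged clinically significant; sponsor informed |
| 8.1.1, investigator decision | Drug may be stopped for such a value; sponsor alerted |
| 9.4.3 | Sponsor reviews aggregate laboratory trends |
| Appendix 4 | Liver tests may be obtained, and may be required in consultation; no AST threshold or timing |

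All of these permit action. None directs a repeat AST for this patient.

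**The case against.** The strongest reply is that the stopping criterion implies the repeat. An investigator who sees AST above 5×ULN cannot apply a two-week rule without testing again, and several routes let that investigator retest, interrupt or stop the drug at once. This stands as a reason to keep the point small. It does not remove it, because each route rests on individual judgment, whereas the same rise in ALT has a written retest instruction.

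A second reply is that this is a design choice. Exclusion criterion [17] also uses ALT alone, and a retest trigger may be narrower than a list of discretionary considerations. An isolated AST rise may also come from outside the liver, and creatine kinase is already in the scheduled panel to help interpret it. That is fair, but 8.1.1 does not follow an ALT-only approach: it lets AST count alone at >8×ULN and at >5×ULN sustained.

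A third reply is that the gap shown starts at 5×ULN while the proposed trigger is 3×ULN. That is correct. The lower value is chosen to mirror the ALT trigger, and 3×ULN is also an AST level in the combined conditions of 8.1.1.

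Two stronger readings are tempting and should not be drawn. A reader might set the 112 days for AST against the earliest possible ALT answer and quote a ratio. That compares a worst case for AST with a best case for ALT. Both paths rest on advisory wording or judgment, and the ALT monitoring frequency is unstated. A reader might also infer that 9.4.3.1.1 contributes to the missing retest. It governs only which extra data are recorded and orders no test. AST values are in any case tabulated in the shift tables of SAP 6.10.4.

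**Conclusion.** The mismatch is real and narrow. For an isolated AST of >5 to 8×ULN at Week 36, in a patient meeting all the conditions listed in the working, no repeat is directed before the Week 52 panel. The scheduled gap is 16 weeks (14 to 18 with windows).

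This assumes that the patient stays in the study and on drug, and that nobody uses the discretionary routes. It is therefore the interval the schedule allows, not a prediction of delay. The documents give no rate of isolated AST rises, so no number of affected patients can be stated. The 8.1.1 liver conditions are themselves considerations, not mandatory stops.

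This is a cheap improvement to patient-safety follow-up, with no effect on the primary endpoint, alpha, power or SAP analyses.

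**What to change.** In Protocol 9.4.3.1, make the aminotransferase trigger **ALT or AST ≥3×ULN**. This is the one edit that closes the gap. It needs no new assay or scheduled visit, because AST is already in the chemistry panel and in the retest list. The cost is a number of extra retests that the documents do not allow one to estimate, some of them for AST rises of non-liver origin. The edit adds no scheduled chemistry before Week 36.

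Optionally, and only for consistent data collection, make the condition in 9.4.3.1.1 **ALT or AST ≥5×ULN** on the same two-consecutive-test basis. This second edit does not affect retesting.

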9.4.3.1.1. Hepatic Safety Data Collection

Additional safety data should be collected via the eCRF if 1 or more of the following conditions occur:

- elevation of serum ALT to $\geq 5 \times \text{ULN}$ on 2 or more consecutive blood tests
- elevated serum total bilirubin to $\geq 2 \times \text{ULN}$ (except for cases of known Gilbert's syndrome)

- elevation of serum alkaline phosphatase to $\geq 2 \times \text{ULN}$ on 2 or more consecutive blood tests
- patient discontinued from treatment due to a hepatic event or abnormality of liver tests
- hepatic event considered to be a SAE

9.5. Pharmacokinetics

Venous blood samples of approximately 4 mL for determining plasma concentrations of dulaglutide, associated with time from dose, will be obtained at selected visits from all patients in accordance with the Study Schedule (Section 2). Instructions for the collection and handling of blood samples will be provided by the sponsor. The actual date and time (24-hour clock time) of each sampling and all study drug doses must be clearly recorded.

A PK sample can be collected at any time during those clinic visits at which an immunogenicity sample is to be taken, and at ET visits.

The study has been designed so that, where possible, each immunogenicity sample will be accompanied by a PK sample in the same visit (except for Visit 3 [baseline]). At visits where ECG measurements are also taken, these should be accompanied by a time-matched PK sample within 30 minutes after the ECG measurement, during the same visit.

Drug concentration information that would unblind the study will not be reported to investigative sites or blinded personnel until the study has been unblinded.

Bioanalytical samples collected to measure investigational product concentration will be retained for a maximum of 1 year following last patient visit for the study.

9.6. Pharmacodynamics

Pharmacodynamic parameters will include safety and efficacy endpoints as described in Section 4. Analysis methods are described in Section 10.3.5.

9.7. Pharmacogenomics

9.7.1. Whole Blood Samples for Pharmacogenetic Research

A whole blood sample will be collected for pharmacogenetic analysis as specified in the Schedule of Activities (Section 2) where local regulations allow.

Samples will not be used to conduct unspecified disease or population genetic research either now or in the future. Samples will be used to investigate variable response to dulaglutide and to investigate genetic variants thought to play a role in T2D and related complications. Assessment of variable response may include evaluation of AEs or differences in efficacy.

All samples will be coded with the patient number. These samples and any data generated can be linked back to the patient only by the investigator site personnel.

Samples will be retained at a facility selected by Lilly or its designee for a maximum of 15 years after the last patient visit for the study, or for a shorter period if local regulations and/or ERBs impose shorter time limits. This retention period enables use of new technologies, response to regulatory questions, and investigation of variable response that may not be observed until later in the development of dulaglutide.

Molecular technologies are expected to improve during the 15-year storage period and therefore cannot be specifically named. However, existing approaches include whole genome or exome sequencing, genome-wide association studies, and candidate gene studies, and epigenetic analyses. Regardless of technology utilized, genotyping data generated will be used only for the specific research scope described in this section.

9.8. Biomarkers and Antibodies

9.8.1. Samples for Immunogenicity Research

Samples from patients in each treatment arm will be tested for the development of dulaglutide ADA. A blood sample will be collected at specific study visits according to the Schedule of Activities (Section 2), along with a simultaneous drug concentration sample.

Samples with dulaglutide ADA detected will be titered and evaluated for their ability to neutralize the activity of assigned treatment (dulaglutide-neutralizing antibodies). Samples with dulaglutide ADA detected will also be tested for cross-reactive-binding to native GLP-1, and if such is detected, then for neutralizing antibodies against native GLP-1.

Samples will be retained for a maximum of 15 years after the last patient visit for the study, or for a shorter period if regulations and ERBs impose shorter time limits, at a facility selected by Lilly or its designee. The duration allows the sponsor to respond to future regulatory requests related to dulaglutide.

9.8.2. Biomarkers

Biomarker research is performed to address questions of relevance to drug disposition, target engagement, PD, mechanism of action, variability of subject response (including safety), and clinical outcome. Sample collection is incorporated into clinical studies to enable examination of these questions through measurement of biomolecules including proteins, lipids, and other cellular elements.

Serum and plasma samples (ethylenediaminetetraacetic acid [EDTA] and remaining P800 plasma from glucagon collection) for nonpharmacogenetic biomarker research will be collected at the times specified in the Schedule of Activities (Section 2) where local regulations allow.

Samples will be used for research on the drug target, disease process, variable response to dulaglutide, pathways associated with diabetes mellitus, mechanism of action of dulaglutide, and/or research method, or for validating diagnostic tools or assay(s) related to diabetes mellitus.

All samples will be coded with the subject number. These samples and any data generated can be linked back to the subject only by the investigative site personnel.

Samples will be retained for a maximum of 15 years after the last subject visit, or for a shorter period if local regulations and/or ERBs impose shorter time limits, at a facility selected by Lilly. This retention period enables use of new technologies, response to regulatory questions, and investigation of variable response that may not be observed until later in the development of dulaglutide or after dulaglutide is commercially available.

